## **7.3 GENE EXPRESSION PROFILING**

### **7.3.1 Whole Blood–Gene Expression Profiling**

Previous gene profiling studies in biopsy material of transplant recipients indicate that changes in expression of a panel of genes, as measured by quantitative real-time PCR (RT-PCR) or DNA microarrays can be predictive of acute allograft rejection. These genes include perforin, cyclooxygenase, and IL-7, among others. Interestingly, some studies indicate that these changes are also measurable by RT-PCR of RNA made from peripheral blood.

Additionally, peripheral blood RNA samples taken just before withdrawal of immunosuppression, during withdrawal, and post withdrawal will be measured on microarray and RT-PCR to see if we can discover new patterns of genes that indicate tolerance-like state or a predisposition to tolerance vs. rejection before drug withdrawal. Both microarray and high-throughput quantitative RT-PCR will be used to define global changes in gene expression. Monitoring during withdrawal of immunosuppression will allow the detection of changes in gene expression patterns predictive of, or correlated with, rejection. Peripheral blood expression of acute rejection–associated genes will be complemented by profiles of these same genes in protocol-directed or clinically indicated liver biopsies.

### **7.3.2 Liver Biopsy RNA–Gene Expression Profiling**

Transcriptional profiling will be performed at time points described in the schedule of events (see Appendices 1–3). Total RNA will be isolated and analyzed for expression of selected immune response genes related to rejection and immunoregulatory functions, including granzyme B, cyclooxygenase, IFN $\gamma$ , TGF- $\beta$ , IL-4, IL-7, IL-10, and IL-15. In addition, we will study genes, such as FoxP3, which may indicate immune regulation in the liver. The success or failure of immunosuppression withdrawal will be correlated with the expression of both rejection-associated genes and immune regulation genes. The analysis will be performed using TaqMan® RT-PCR at the ITN Core Laboratory.

## **7.4 SERUM ASSAYS**

### **7.4.1 Serum–Secreted Cytokines**

Levels of various immune cytokines will be measured in participant's serum to determine if cytokine levels are linked to induction of clinical tolerance or are indicative of allograft rejection. Serum will

be collected at regular intervals during the study as well as at the time of clinically directed biopsies. The cytokines analyzed will include IL-2, IL-5, IL-10, TNF- $\alpha$ , and IFN- $\gamma$ . Higher levels of IL-2, TNF- $\alpha$ , and IFN- $\gamma$  are indicative of a TH1-mediated immune response. Higher levels of IL-5 and IL-10 are indicative of a TH2-mediated immune response.

By using a multianalytical profiling system, the quality, sensitivity, and throughput of cytokine and chemokine assays can be improved.

#### **7.4.2 Serum–HLA Alloantibodies**

Donor-specific alloantibodies have been shown to be less of a risk factor for graft rejection in liver transplant recipients than in recipients of other organ allografts. Their presence, however, may preclude development or signal the absence of functional tolerance. Serum samples collected from participants, therefore, will be evaluated for the presence or absence of donor-specific alloantibodies.

Alloantibody assessments will be performed before immunosuppression withdrawal (baseline) and at selected time points during and after withdrawal. Assessments will include donor-specific cross matching with cryopreserved cells, testing against a panel of cryopreserved lymphocytes or HLA antigen-coated microparticles.

## **8. ADVERSE EVENTS**

### **8.1 OVERVIEW**

Safety data will be recorded on a case report form (CRF) specifically designed for this purpose. All the SAE information will be recorded on the source document and transcribed onto an SAE report; pertinent data will be collected on the appropriate CRF. All data will be reviewed periodically by the Data and Safety Monitoring Board (DSMB). The DSMB has the authority to withdraw any participants and/or terminate the study because of safety concerns.

Adverse events that are classified as serious according to the definition of health authorities must be reported promptly and appropriately to the NIAID, ITN, principal investigators in the trial, IRBs, and health authorities. This section defines the types of adverse events and outlines the procedures for appropriately collecting, grading, recording, and reporting them. Information in this section complies with *ICH Guideline E2A: Clinical Safety Data Management: Definitions and Standards for Expedited Reporting*, *ICH Guideline E-6: Guideline for Good Clinical Practice*, and applies the standards set forth in the National Cancer Institute (NCI), *Common Terminology Criteria for Adverse Events*, Version 3.0 (June 10, 2003).

### **8.2 DEFINITIONS**

#### **8.2.1 Adverse Event**

An adverse event is any occurrence or worsening of an undesirable or unintended sign, symptom, laboratory finding, or disease that occurs during participation in the trial. An adverse event will be followed until it resolves or until 30 days after a participant terminates from the study, whichever comes first.

### 8.2.2 Serious Adverse Event

A serious adverse event (SAE) or reaction is defined as “any adverse event that suggests a significant hazard, contraindication, side effect, or precaution.” This includes, but is not limited to, any of the following events:

- Death: A death that occurs during the study or that comes to the attention of the investigator during the protocol-defined follow-up period must be reported whether it is considered treatment related or not.
- A life-threatening event: Any adverse experience that, in the view of the investigator, places the participant at immediate risk of death.
- Inpatient hospitalization or prolongation of existing hospitalization.
- Persistent or significant disability.
- An event that requires intervention to prevent permanent impairment or damage. An important medical event that may not result in death, be life threatening, or require hospitalization may be considered an SAE when, based on appropriate medical judgment, it may jeopardize the participant and may require medical or surgical intervention to prevent one of the outcomes listed above.
- Congenital anomaly or birth defect.

Regardless of the relation of the adverse event to study participation, the event must be reported as an SAE if it meets any of the above definitions.

### 8.2.3 Unexpected Adverse Events

An adverse event is considered “unexpected” when its nature (specificity) or severity is not consistent with the usual clinical course of individuals who would qualify for this trial but who were not enrolled.

## 8.3 COLLECTING ADVERSE EVENTS

### 8.3.1 Methods of Collection

Adverse events will be collected from the time consent is obtained from the participant until the time the event resolves or until he/she completes study participation, whichever comes first.

Adverse events may be discovered by any of these methods:

- Observing the participant.
- Questioning the participant in an objective manner.
- Receiving an unsolicited complaint from the participant.

An abnormal value or result from a clinical or laboratory evaluation (e.g., a radiograph, an ultrasound, or an electrocardiogram) can also indicate an adverse event if it is determined by the investigator to be clinically significant. If this is the case, it must be recorded in the source document and as an adverse event on the appropriate adverse event form(s). The evaluation that produced the value or result should be repeated until that value or result returns to normal or can be explained and the participant’s safety is not at risk.

### 8.3.2 Collecting Serious Adverse Events

Serious adverse events will be collected from the time the participant begins study participation until 30 days after he/she completes or prematurely withdraws from the study.

### 8.3.3 Recording Adverse Events

Throughout the study, the investigator will record all adverse events on the appropriate adverse event case report form (CRF) regardless of their severity or relation to study participation. The investigator will treat participants experiencing adverse events appropriately and observe them at suitable intervals until their symptoms resolve or their status stabilizes.

### 8.3.4 Recording Serious Adverse Events

Serious adverse events will be recorded on the adverse event CRF and on the SAE form, and health authorities will be notified as outlined in section 8.5.

## 8.4 GRADING AND ATTRIBUTION OF ADVERSE EVENTS

### 8.4.1 Grading Criteria

The study site will grade the severity of adverse events experienced by study participants according to the criteria set forth in the National Cancer Institute's Common Toxicity Criteria for Adverse Events Version 3.0 (published June 10, 2003). This document (referred to herein as the NCI-CTCAE manual) provides a common language to describe levels of severity, to analyze and interpret data, and to articulate the clinical significance of all adverse events.

Adverse events will be graded on a scale from 1 to 5 according to the following standards in the NCI-CTCAE manual:

- Grade 1 = mild adverse event.
- Grade 2 = moderate adverse event.
- Grade 3 = severe and undesirable adverse event.
- Grade 4 = life-threatening or disabling adverse event.
- Grade 5 = death.

All adverse events will be reported and graded whether they are or are not related to disease progression or study participation.

### 8.4.2 Attribution Definitions

The relation, or attribution, of an adverse event to study participation will be determined by the site investigator. The site investigator will also record the determination of attribution on the appropriate CRF and/or SAE reporting form. The relation of an adverse event to study participation will be determined using the descriptors and definitions provided in Table 6.

For additional information and a printable version of the NCI-CTCAE manual, consult the NCI-CTCAE web site: <http://ctep.cancer.gov/reporting/ctc.html>.

**Table 6. Attribution of adverse events**

Code	Descriptor	Definition
Unrelated Category		
1	Unrelated	The adverse event is clearly not related to study participation.

Related Categories		
2	Unlikely	The adverse event is doubtfully related to study participation.
3	Possible	The adverse event may be related to study participation.
4	Probable	The adverse event is likely related to study participation.
5	Definite	The adverse event is clearly related to study participation.

## 8.5 REPORTING SERIOUS ADVERSE EVENTS

### 8.5.1 Reporting Timeline

When an investigator identifies a serious adverse event (as defined in section 8.2.2), he or she must notify the Rho Federal Systems Division, Inc. (Rho Fed) Safety Reporting Center within 24 hours of discovering the event using the Rho Fed 24-Hour SAE Reporting [contact])**. In addition to being reported by telephone, these events will be entered on the serious adverse event form and the adverse event CRF. Both forms will be faxed to the Rho Fed Safety Reporting Center **([name])** or **E-MAIL** ([rho\\[contact]](mailto:[contact])). within 24 hours. Rho Fed is responsible for notifying the sponsor within 48 hours of receipt of the event.

### 8.5.2 Options for Reporting Serious Adverse Events

After the SAE has been assessed by the investigator, there are three options for reporting an event to the appropriate health authorities:

- **No requirement to report.** This option applies if the adverse event is deemed not serious by the Rho Fed Safety PSS, the ITN clinical physician and the NIAID medical monitor.
- **Standard reporting is required.** This option applies if the adverse event is classified as one of the following: (a) serious, expected, and study related; (b) serious, expected, and not study related; or (c) serious, unexpected and not study related.
- **Expedited reporting is required.** This option applies if the adverse event is considered serious, unexpected, and study related. These events must be reported by the sponsor to the appropriate health authorities within 15 days; fatal or life-threatening events must be reported within 7 days. For expedited SAEs, all sites must attach the notification letter and MedWatch/CIOMS to the current investigator's brochure.

All investigators must report serious adverse events to their respective IRBs as mandated by them.

### 8.5.3 Reporting Serious Adverse Events to the Data Safety Monitoring Board

The DSMB will be provided listings of all SAEs on an ongoing basis. Furthermore, the DSMB will be informed of expedited SAEs by the Regulatory CRO at the same time as health authorities.

### 8.5.4 Reporting Pregnancy

Any pregnancy that occurs during a clinical study will be reported on an SAE form for tracking purposes only. The investigator should be informed immediately of any pregnancy and should report all pregnancies within 24 hours (as described in section 8.5.1) using the SAE form. The investigator should counsel the participant and discuss the risks of continuing with the pregnancy and the possible

effects on the fetus. Monitoring of the participant should continue until the conclusion of the pregnancy, and a follow-up SAE reporting form detailing the outcome of the pregnancy should be submitted.

## **9. STATISTICAL CONSIDERATIONS AND ANALYTICAL PLAN**

### **9.1 ANALYSIS SAMPLES**

The following groups of participants will define samples for endpoint analysis:

- Intent-to-treat (ITT) sample: Subjects who have signed informed consent and are enrolled.
- Per-protocol (PP) sample: All participants in whom immunosuppression withdrawal is attempted.

### **9.2 ANALYSIS PLAN**

#### **9.2.1 Analysis of Primary Endpoint**

The proportion of participants who are successfully withdrawn from immunosuppression, defined as those who remain off immunosuppression for at least 1 year, will be analyzed using the PP sample and descriptively summarized with a two-sided, 95% CI. Participants with acute rejection occurring after 1 year following complete immunosuppression withdrawal will be considered successfully withdrawn for the purpose of the primary endpoint. This endpoint will also be analyzed using the ITT sample.

#### **9.2.2 Analysis of Secondary Endpoints**

##### **9.2.2.1 Safety of Immunosuppression Withdrawal**

The following endpoints will be analyzed using the PP and ITT samples:

- The proportion of participants who have graft loss or who die after initiation of immunosuppression withdrawal will be descriptively summarized with a two-sided, 95% CI.
- Median time from initiation of immunosuppression withdrawal to first episode of acute rejection or to first diagnosis of chronic rejection, with a corresponding two-sided 95% CI, will be estimated using the Kaplan-Meier method.
- Distribution of severity among rejection episodes and the incidence of adverse events will be descriptively summarized using frequency tables with enumerations and percentages.
- Descriptive statistics (mean, standard deviation, mean change from baseline) for renal function, blood pressure, cholesterol level, and glucose control over time will be presented.

##### **9.2.2.2 Duration**

Median immunosuppression-free duration with a corresponding two-sided 95% CI will be estimated with the Kaplan-Meier method using the PP and ITT samples.

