#### **3.3.2 Secondary Endpoints**

##### **3.3.2.1 Safety of Immunosuppression Withdrawal**

1. The proportion of participants who have graft loss or who die after initiation of immunosuppression withdrawal.
2. The time from the start of immunosuppression withdrawal to
  - a. the first episode of acute rejection requiring treatment,
  - b. the second episode of acute rejection not requiring treatment, or
  - c. the diagnosis of chronic rejection.
3. The distribution of histologic severity among rejection episodes.
4. The incidence of adverse events.
5. Changes in renal function, blood pressure, cholesterol level, and glucose control.

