##### **3.3.2.2 Duration**

Immunosuppression-free duration, defined as the time from discontinuation of immunosuppression to end of trial participation or to time of restarting immunosuppression.

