3.2.2 Secondary Endpoints

The following secondary endpoints are related to the safety of immunosuppression withdrawal.

- The proportion of subjects who have graft loss or who die after initiation of immunosuppression withdrawal.
- The time from the start of immunosuppression withdrawal to
 - the first episode of acute rejection requiring treatment,
 - the second episode of acute rejection not requiring treatment, or
 - the diagnosis of chronic rejection.
- The distribution of histologic severity among rejection episodes.
- The incidence of adverse events.
- Changes in renal function, blood pressure, cholesterol level, and glucose control.

Other secondary endpoints include

- Immunosuppression-free duration, defined as the time from discontinuation of immunosuppression to end of trial participation or to time of restarting immunosuppression;
- Results of mechanistic studies and clinical assessments at various time points that allow for the definition of profiles associated with tolerance;
- Results of mechanistic studies and clinical assessments that allow for definition of profiles associated with liver allograft rejection.

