9.2.2 Secondary Efficacy Variables

1) Immunosuppression-free duration: a continuous variable measured in days and is defined as: date of end of trial participation or date of restarting immunosuppression – date of completing withdrawal. All subjects completing withdrawal at any time will be included.

2) Time to Rejection: time from initiation of immunosuppression withdrawal to first episode of acute rejection or first diagnosis of chronic rejection measured in days and defined as date of first episode of acute rejection or date of first diagnosis of chronic rejection – date of

initiation of immunosuppression withdrawal. All subjects initiating withdrawal (PP1 sample) will be included.

3) Graft Loss or Death:

Proportion of subjects who have graft loss or who die after initiation of immunosuppression withdrawal: a continuous variable taking on values between 0 and 1, the numerator is the total number of subjects who experience either graft loss or death after initiation of immunosuppression withdrawal and the denominator is the total number of subjects initiating immunosuppression withdrawal (PP1 sample). This analysis will also be done on the PP2 sample.

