9.3.2 Secondary Efficacy Analyses

- 1) Median immunosuppression-free duration will be estimated for all subjects completing withdrawal. Duration will be displayed graphically with a Kaplan-Meier curve and the corresponding median and two-sided 95% confidence interval.
- 2) Median time from initiation of immunosuppression withdrawal to first episode of acute rejection or to first diagnosis of chronic rejection will be estimated for the PP1 sample. Duration will be displayed graphically with a Kaplan-Meier curve and the corresponding median and two-sided 95% confidence interval.
- 3) The proportion of subjects experiencing graft loss or death after initiation of immunosuppression withdrawal will be descriptively summarized for the PP1 and PP2 samples as well as the ITT sample with 95% confidence intervals using an exact binomial method.

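### Time to rejection is analysed on a different event from the one defined, and the protocol analyses immunosuppression-free duration in samples where some participants have no start date

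*Protocol*

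**What the plan says.** **Rejection, as defined.** Protocol 3.3.2.1 and SAP 3.2.2 list the same three-part event, timed from the start of withdrawal: "the first episode of acute rejection requiring treatment", "the second episode of acute rejection not requiring treatment", or a diagnosis of chronic rejection.

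**Rejection, as analysed.** Protocol 9.2.2.1 and SAP 9.2.2 and 9.3.2 (item 2) estimate the median time to any first acute rejection or first chronic rejection. The treated/untreated distinction is gone. The protocol uses PP and ITT. The SAP uses PP1: "All subjects initiating withdrawal (PP1 sample) will be included".

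**Duration, as defined.** Protocol 3.3.2.2 measures "the time from discontinuation of immunosuppression to end of trial participation or to time of restarting immunosuppression".

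**Duration, as analysed.** Protocol 9.2.2.2: "Median immunosuppression-free duration with a corresponding two-sided 95% CI will be estimated with the Kaplan-Meier method using the PP and ITT samples". SAP 9.3.2 (item 1): "Median immunosuppression-free duration will be estimated for all subjects completing withdrawal". SAP 9.2.2 agrees with the latter: "All subjects completing withdrawal at any time will be included". SAP Table 9-1 names the same sample.

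**Output.** For both endpoints, SAP 9.3.2 says: "Duration will be displayed graphically with a Kaplan-Meier curve and the corresponding median and two-sided 95% confidence interval". SAP section 14, on changes from the protocol's planned analyses, records neither the change of duration sample nor the change of rejection sample.

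**The concern.** Safety and durability of withdrawal are both secondary objectives, and these two analyses carry much of the answer.

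For rejection, the mismatch affects who counts. Under protocol 5.5.3.2, a participant whose first mild episode resolves untreated may resume withdrawal and can go on to be a primary-endpoint success. The analysis text counts that participant as a rejection; the definition does not. A participant with an untreated episode followed later by a treated one is an event under both texts, but on different dates.

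For duration, the mismatch affects the denominator. PP is everyone in whom withdrawal is attempted, including those who never come off drug. ITT adds a further ambiguity: protocol 3.6 starts enrollment on the day withdrawal begins, while SAP section 5 starts it at screening, so the SAP's ITT sample can include people who never began withdrawal.

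Two analysts, each following a different part of these texts, could report different event counts and different denominators from the same data.

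**Working it through.** **1. The plan's own figures.** Protocol 9.3 and SAP 3.7 give exact binomial intervals for x successes in n = 20. Lower limit = 0.025 quantile of Beta(x, n−x+1); upper limit = 0.975 quantile of Beta(x+1, n−x).
- 9/20: 23.1–68.5%. 4/20: 5.7–43.7%. Both match.
- Wald limits (23.2–66.8% and 2.5–37.5%) and Wilson limits (25.8–65.8% and 8.1–41.6%) do not, so the exact method was used as stated.

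**2. Rejection: the two events compared.**

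| Participant's course | Event as defined | Event as analysed |
|---|---|---|
| One treated acute rejection | Yes | Yes |
| Chronic rejection | Yes | Yes |
| Two untreated acute rejections | Yes, at the second | Yes, at the first |
| One untreated mild rejection, resolved | No | Yes |

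Each participant in the last row moves the crude proportion by 1/20 = 5 points. Illustration with two such participants, all 20 in PP1 and no censoring (exact limits):
- As analysed: 8/20 = 40% (19.1–63.9).
- As defined: 6/20 = 30% (11.9–54.3).

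**3. Duration: can PP be used?** Not as written, because there is no start date for those who never stop. Suppose a zero-duration rule were added (an assumption; neither document has one). The PP curve would then start at c/20 with c completers: 4/20 = 20%, 9/20 = 45%. With 9 or fewer completers it starts below 50%, so the median is 0 days whatever happens afterwards. It would describe failure to complete, not durability.

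**4. Will the completers' median be reached?** Follow-up after completion is 12 + 104 + 104 = 220 weeks (220/52 = 4.2 years) on the schedule common to both documents. It is 220 + 208 = 428 weeks (8.2 years) with the protocol's extension. With n completers, a constant annual restart rate r, follow-up of T years and no dropout, the probability that a participant restarts by T is p = 1 − (1 − r)^T. The median is reached if at least n/2 restart (rounded up), so

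P(not reached) = 1 − P(Bin(n, p) ≥ ⌈n/2⌉).

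Example: n = 9, r = 10%, T = 4.23 gives p = 0.36 and P(not reached) = 0.81. The documents give no restart rate, so r is assumed; the ranges cover n = 4 to 14.

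| Assumed r per year | Not reached at 4.2 years | Not reached at 8.2 years |
|---|---|---|
| 2% | 96–100% | 89–100% |
| 5% | 83–99% | 57–84% |
| 10% | 55–81% | 19–31% |
| 20% | 13–24% | 0–1% |

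**5. Precision of a fixed-time proportion (log-log limits, no earlier censoring).** 9 completers with 1 restart: 88.9% (43.3–98.4). 4 completers with 1 restart: 75% (12.8–96.1). Estimable, but wide.

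**The case against.** **Version lag.** SAP section 13 cites protocol version 4.0, and SAP 3.4 gives 4 years of follow-up where protocol 3.1 gives 8. An older base text could explain the difference in samples. It cannot explain the rejection mismatch, which sits inside each document.

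**Rejection is already reported elsewhere.** A reader might infer that a curve and a median are all the plan offers on rejection. That is not so. SAP 6.1 tabulates reasons for discontinuing withdrawal, with treated rejection, second untreated mild rejection and chronic rejection as separate categories; SAP 10.4.2 summarises severity; SAP 10.4.4 lists dysfunction episodes and whether rejection was treated. This stands and limits the consequence. It does not settle which event the time-to-event analysis uses, and the 6.1 reasons concern stopping withdrawal, not rejection after completing it.

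**PP could be made to work.** A reader might infer that completers are the only possible sample. A zero-duration rule would make PP computable, though uninformative about durability at plausible completion counts. Completers is a reasoned choice. It is also a selected group, so the result has to be labelled as conditional.

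**Censoring.** It is tempting to say that time to rejection has no censoring rule. SAP 9.1.1 speaks of Kaplan-Meier analyses and mentions time off immunosuppression in parentheses, which may be only an example. The text is unclear, not plainly absent.

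**Fixed-time proportions are a preference.** Largely true. The curve is planned, and with at most 20 participants such proportions can be read from it.

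**Conclusion.** Two mismatches between endpoint and analysis are confirmed from the text alone. The rejection event analysed in both documents is broader than the one both define, at 5 percentage points per affected participant. The number affected is unknown in advance; two is an illustration. The protocol's duration samples include participants for whom duration is undefined, while the SAP's sample fits the definition.

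A stronger reading would be that the planned median will fail. The documents do not support it: non-attainment ranges from near certain to near zero, depending on a restart rate they do not give and on whether follow-up is 4.2 or 8.2 years. Nor is the main result touched: the primary endpoint is a proportion in PP1 and PP2 with its own definition, and N = 20 rests on its precision. Severity is minor, and the analyses are descriptive.

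**What to change.** 1. **Rejection.** In protocol 9.2.2.1 and SAP 9.2.2, 9.3.2 and Table 9-1, analyse the three-part event as defined in protocol 3.3.2.1 and SAP 3.2.2, in PP1. Keep any first acute or chronic rejection as a supportive analysis. Extend the censoring sentence in SAP 9.1.1 to name time to rejection.
2. **Duration.** In protocol 9.2.2.2, replace PP and ITT with participants who complete withdrawal. Label the estimate as conditional on completing, and show the number completing out of PP1 beside it. Add one line to SAP 9.2.2: restarting immunosuppression is the event, and those still off drug are censored when last known to be off drug.
3. **Record.** List the changes in SAP section 14.
4. **Optional.** Add Kaplan-Meier proportions off drug at 2 and 4 years among completers, with numbers at risk and 95% CIs, and name the interval method. Set later times only once the 4-year and 8-year follow-up statements are reconciled.

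The cost is wording and, if item 4 is taken up, a few table rows from the same Kaplan-Meier output; no extra visits, data or participants. The amendment steps still apply: protocol 9.7 sends changes to principal features to the DSMB, sponsor and regulators, and 12.1 requires ethics approval of protocol amendments. The protocol wording could reasonably travel with the next amendment.
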